1. HYPOTHESIS

Pathologic complete response (pCR) is associated with improved survival and lower risk for distant metastases. Neoadjuvant Endo-HDR will increase pCR rates compared to concurrent chemoradiation (RT + Capecitabine). We expect similar locoregional control, decreased treatment time (1 week as opposed to 6 weeks), improved sphincter preservation rates, and lower acute and chronic toxicity.

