3. BACKGROUND

3.1 Rationale

Locally advanced rectal carcinoma continues to be a major oncologic problem in the United States with approximately 40,000 new cases diagnosed in 2012. For stage II/III rectal carcinoma, adjuvant chemoradiation (1-3) and total mesorectal excision (TME) (4, 5) represent the major treatment advances that have increased cure rates over the past 30 years.

In the setting of TME, a landmark phase III German trial of stage II/III rectal cancer patients established neoadjuvant 5FU-based chemoradiation (NCRT) as standard of care over the same regimen given post-operatively (6). The preoperative arm showed superior local control (6% vs. 13% p=0.006), a complete pathologic response of 8%, a higher rate of sphincter preservation and less grade 3 toxicity compared to post-operative treatment. However, disease-free and overall survival (76% versus 74%, respectively) were no different because of the high rate of distant metastasis occurring in over 1/3 of patients (5yr DM 36 vs 38%, p=0.84). Importantly, those attaining a pathologic complete response had a decreased rate of distant metastasis and improved disease-free survival. Drawbacks to the regimen include acute grade 3 or 4 toxicity in 27% of patients, low compliance rates with postoperative chemotherapy (27 – 50%), and an overall decline in anorectal function shown by long-term studies (6).

Given the excellent locoregional control reported in TME surgical series, several trials have investigated whether certain patients may be spared preoperative radiotherapy (7-9). Two large randomized trials by Dutch and British investigators showed that a short preoperative course of hypofractionated EBRT (25 Gy in 5 fractions) followed by TME surgery decreased locoregional recurrence by 2/3 as compared to patients treated with TME surgery alone. In the Dutch trial, patients with mid and distal rectal cancers were most likely to benefit from radiotherapy. In these patients, preoperative radiation was shown to decrease locoregional recurrence by 5-fold (10% to 2%); however, the

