4.2 Secondary Objectives

- Test whether clinical response based on functional imaging (PET, MRI) pre/post radiation (Endo-HDR vs. CRT) predicts for pathologic complete response.
- Utilize preoperative imaging response rates and clinical exam to determine whether Endo-HDR results in improved sphincter preservation rates when compared to CRT.
- Determine whether tumor (VEGF/EGFR status) and blood predict for pathologic response following neoadjuvant Endo-HDR vs. CRT.
- Compare acute and long-term toxicity as well as quality of life for both Endo-HDR and CRT.
- Compare locoregional control, distant metastasis and overall survival for both Endo-HDR and CRT.

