14.5 Analysis of Secondary Endpoints

Secondary endpoints of this phase II trial include toxicity, quality of life, locoregional control/distant metastasis, overall survival, and correlative analyses of biomarkers and functional imaging changes.

The acute and chronic toxicity and adverse events will be summarized in frequency tables by type and grade for each arm and will be compared between arms using Fisher's exact tests.

Quality of life will be assessed via EORTC QLQ-C30 (v3.0) questionnaires as mentioned above. Scoring will be based on procedures outlined by the EORTC. For our study population of rectal cancer patients, the analysis will be focused on general and colorectal model regarding urinary/bowel toxicity, sphincter function, and sexual dysfunction. For each module, summary statistics of the scores will be reported at baseline and each follow-up time. After confirming that there are no baseline differences in quality of life across the two treatment arms using independent samples t-test, changes in quality of life scores from pre- to post-treatment will be computed, and the difference between these change scores will be evaluated by paired-sample t-tests. We will compare the quality of life scores at each endpoint as well as the differences between the two arms using two-sample t-test. Given the plurality of comparisons, p-values <0.01 will be considered statistically significant. In addition, mixed effect models will be used for assessing the quality of life change over time and comparing the two treatment arms. For instance, mixed effects models will be used to assess changes in QOL over time first in all study patients and then to compare the effects of the two treatment arms on change in QOL over time. Need for sexual aids will be compared in a descriptive fashion between the two cohorts.

Overall survival, distant metastases free survival, progression free survival, and local recurrence will be measured from the date of randomization to the date of death due to any causes. Patients last known to be alive are censored at date of last contact. Kaplan-Meier curves will be used to characterize overall survival in each arm and log rank test will be used for the comparison.

The analysis of correlative endpoints of imaging and biomarkers will be exploratory.

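### Section 14.5 gives distant-metastases-free survival, progression-free survival and local recurrence the overall-survival event, so the planned comparison of locoregional control and distant metastasis has no valid analysis as written

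*Combined protocol and SAP*

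**What the plan says.** Section 4.2 sets the objective: "Compare locoregional control, distant metastasis and overall survival for both Endo-HDR and CRT". The endpoint list in Section 14.5 keeps these items apart: "Secondary endpoints of this phase II trial include toxicity, quality of life, locoregional control/distant metastasis, overall survival". Section 1 states an expectation for one of them: "We expect similar locoregional control".

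The measurement rule in Section 14.5 opens with overall survival and distant-metastases-free survival and continues: "progression free survival, and local recurrence will be measured from the date of randomization to the date of death due to any causes". One censoring rule follows: "Patients last known to be alive are censored at date of last contact". The only method named is for overall survival: "Kaplan-Meier curves will be used to characterize overall survival in each arm and log rank test will be used for the comparison".

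The objective and the endpoint list speak of locoregional control, while the rule speaks of local recurrence. Neither says whether pelvic nodal failure is included.

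**The concern.** Death from any cause, with living patients censored at last contact, is the right definition for overall survival and for none of the other three. Applied literally, it makes the disease endpoints blind to the disease events they are named after.

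This matters for this trial in particular. The experimental arm omits elective external-beam treatment of the pelvic nodes. Section 3.1 itself raises more pelvic nodal recurrence as a theoretical concern, while citing low rates in modern surgical series. Similar locoregional control is part of the hypothesis. If local recurrence differed between arms and survival did not, a test on time to death would reject only at its nominal error rate, and the report would have nothing valid to say on the question.

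**Working it through.** **1. Compare the definitions (Section 14.5).**

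| Endpoint | Origin | Event as written | Censoring as written | Method named |
|---|---|---|---|---|
| Overall survival | randomization | death, any cause | last contact if alive | Kaplan-Meier, log-rank |
| Distant-metastases-free survival | randomization | death, any cause | last contact if alive | none |
| Progression-free survival | randomization | death, any cause | last contact if alive | none |
| Local recurrence | randomization | death, any cause | last contact if alive | none |

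Every patient has the same time and status in all four rows, so any curve or test would repeat the overall-survival result. This step needs no background rate.

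**2. Look for a correction elsewhere.** Section 10.4.2 mentions patterns of recurrence as an outcome, and Sections 3.2.2, 3.2.3 and 10.4.4 mention disease-free survival. None defines an event, its date or its censoring. Section 11.3 excludes signs and symptoms of progression from adverse events, so the safety tables would not supply the information.

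**3. Illustrate the size.** The plan gives no event count or power for these endpoints, so there is no planned figure to reproduce. The inputs are N = 138 (92 + 46, Section 14.2.1) and two sets of background rates from Section 3.1, applied to both arms:

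- Brachytherapy series: local recurrence 5%, overall survival 68%, disease-free survival 65%.
- Preoperative arm of the phase III trial of pre- versus postoperative chemoradiation: local failure 6% ("superior local control (6% vs. 13% p=0.006"), distant metastasis 36%, survival 76% ("disease-free and overall survival (76% versus 74%, respectively) were no different"). The 76% is read as overall survival, because 36% distant metastasis caps disease-free survival at 64%.

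Even if every patient with a recurrence died, deaths without recurrence are at least deaths minus recurrences.

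| Rates used | Recurrences | Deaths | Least share of literal events that are deaths without recurrence |
|---|---|---|---|
| Brachytherapy series | 0.05 × 138 = 6.9 | 0.32 × 138 = 44.2 | (44.2 − 6.9)/44.2 = 84% |
| Chemoradiation arm | 0.06 × 138 = 8.3 | 0.24 × 138 = 33.1 | (33.1 − 8.3)/33.1 = 75% |
| Series in 92, chemoradiation in 46 | 4.6 + 2.8 = 7.4 | 29.4 + 11.0, about 40.5 | 82% |

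Distant metastasis, chemoradiation rates: 0.36 × 138 = 49.7 patients with metastases against 33.1 deaths.

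- Alive with metastases: at least 49.7 − 33.1 = 16.6.
- True distant-metastases-free events: between 49.7 (all deaths among patients with metastases) and 49.7 + 33.1 = 82.8 (no overlap). The written rule counts 33.1.

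If 74% is the right survival figure, deaths are 35.9, the share is at least 77% and the gap at least 13.8. The brachytherapy series gives a smaller gap: 0.35 × 138 = 48.3 disease-free-survival events against 44.2 deaths.

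**4. What a corrected comparison could show.** Assume recurrence of 5% versus 10%, a two-sided 0.05 level (the plan sets none here), 5-year follow-up, exponential times, and deaths of 24% or 32% equal in both arms. Simulated power of a cause-specific log-rank test is about 10–13% if Endo-HDR is the worse arm and about 19–22% if control is. The lower end of each range treats the rates as net of death and the upper end as cumulative incidence. The literal time-to-death test rejects in about 5% of the same runs.

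**The case against.** The strongest reply is that nobody would analyse the data this way. The endpoint names imply their events, the objective and the endpoint list separate them from survival, and the sentence reads like an overall-survival definition stretched over its neighbours. On that view only the dating, censoring, competing deaths and test are unspecified. It is fair that the literal analysis is unlikely to have been intended. But the intended rule cannot be recovered from the text. It remains open whether pelvic nodal failure counts, whether death is an event, a competing event or a censoring for local recurrence, and whether censoring falls at last contact or at last disease assessment. Those choices could end up being made after the data are seen.

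Some narrower objections stand:

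- The event counts come from other studies and are only illustrations. The survival figures carry no printed time point.
- The 5% test level is an assumption.
- A simple event-count formula gives about 20% power when Endo-HDR is worse and 17% when control is worse, the reverse of the simulated order. It should not be relied on under 2:1 allocation.
- Section 7.5 (Follow-Up Assessments) specifies collection of serious adverse events, hospitalizations and quality of life, and the Section 9 calendar has no disease-status row. Recording recurrence may therefore need a case report form item.

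These are secondary endpoints in a phase II trial powered for pCR, which limits the severity but does not remove the error.

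**Conclusion.** The concern holds. As written, the three disease endpoints are overall survival under other names, and the Section 4.2 objective on locoregional control and distant metastasis has no valid analysis. That conclusion follows from the text alone.

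The size is illustrative and assumes that the Section 3.1 rates apply to 138 patients: at least 75–84% of literal local-recurrence events would be deaths without one, and about 14 to 17 or more living patients with metastases would be missed under the chemoradiation rates. The 5% recurrence rate may not transfer. The brachytherapy series gave adjuvant external-beam treatment to node-positive patients and included 7 T4 tumors, whereas Section 2 excludes T4 and Section 7.4.7 lists only FOLFOX after surgery.

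This should be fixed before these endpoints are analysed. It does not touch the primary analysis, the sample size or the interim rule.

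**What to change.** Replace the single sentence in Section 14.5 with separate definitions:

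- **Overall survival:** death from any cause, censored at last contact.
- **Progression-free survival:** first of local progression, distant progression or death.
- **Distant-metastases-free survival:** first of distant metastasis or death.
- **Locoregional recurrence:** first such event, stating whether pelvic nodal failure is included, summarised by cumulative incidence with death without recurrence as a competing event. Use one term throughout.

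Censor event-free patients at the last disease assessment for the disease endpoints. Analyse as randomized, name one between-arm test in advance (Gray's test or a cause-specific log-rank are both acceptable), state its level, and report estimates with confidence intervals. For patients without surgery, whom Section 7.6 follows for survival, say how persistent or progressive disease is classified from standard follow-up.

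The cost is wording plus, at most, a disease-status item on the case report form. Annual CT of chest, abdomen and pelvis is already scheduled for years 1 to 5 in Section 9, so no visits or imaging are added. With so few recurrences expected, the intervals will be wide, and disease status in unresected patients will be only as complete as their routine follow-up.

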14.2 Sample Size/Accrual Rate

14.2.1 Sample Size and Power

We will screen a total of 165 patients for the trial. Based on our phase II single arm endorectal brachytherapy study, we expect approximately 20% of candidates will drop out because of unexpected findings on PET/CT (i.e. metastases) or MRI (i.e. iliac/inguinal lymph nodes). Therefore, we expect to randomize 138 patients in 2:1 ratio into two treatment arms (92 in the Endo-HDR arm and 46 in the control arm). Using a one-sided Fisher's exact test at significance level 0.1, we will have 80% power to detect a 17% increase of pathologic complete response rate from the 13% in the control treatment arm to 30% pCR in the Endo-HDR arm. After randomization, we expect <5% drop-out rate.

One interim analysis for early assessment of futility is planned after 69 patients (half of the total planned sample size) have had their pCR evaluation. The trial will be terminated early if the ratio of the pCR rate in the Endo-HDR arm vs. control arm is 1 or less, i.e., the Endo-HDR treatment appears the same or worse than the control treatment by any amount. This leads to minimal loss of power compared to an analysis without intermediate look.

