For all patients in both study arms, the presence of VEGF/EGFR status will be assessed using pre-treatment tumor biopsies prior to the start of radiation therapy. The result will be expressed as a binary variable indicating the presence of expression (positive/negative). Its association with pCR will be assessed using Fisher's exact test. We will also examine the role of VEGF/EGFR and other hypoxia related biomarkers as a predictive marker for tumor response following Endo-HDR treatment by testing the interaction of the treatment group and VEGF/EGFR status using a logistic regression model where pCR is the dependent variable.

For those treated with Endo-HDR, we anticipate the pCR rate to be 40% among patients with favorable VEGF/EGFR and/or hypoxia marker signature compared to 10% pCR in the group with unfavorable signature. If we observe 40% patients with unfavorable profile, with 92 patients in the Endo-HDR arm, the test will have 89% power.

Prevalence of unfavorable signatures	Power
^a	
^b 25%	0.77
^c 40%	0.89
^e 50%	0.90
^d 75%	0.85

Table 3. Power to detect a 30% difference under various observed prevalence of unfavorable VEGF/EGFR and/or hypoxia marker signatures using a two-sided Fisher's exact test at significance level 0.05.

To assess the correlation of functional PET/MR and treatment response, we will compare the change of SUV pre- and post-treatment between responders and non-responders using a two-sample t-test. Non-parametric Wilcoxon test will be considered when the data are not normally distributed. For a binary response outcome, the predictive ability of the PET/MR marker will be evaluated using an ROC curve based on a logistic regression model in which the imaging marker will be entered as an independent variable.

REFERENCES:

1. Prolongation of the disease-free interval in surgically treated rectal carcinoma. gastrointestinal tumor study group. *N Engl J Med.* 1985 Jun 6; 312(23): 1465-1472.

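### Table 3 states power of 0.77 at 25% unfavorable prevalence, but its own inputs give 0.81; the other three rows reproduce

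*Combined protocol and SAP*

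**What the plan says.** Section 14.5 plans to relate marker status to pCR among patients treated with Endo-HDR. For the better group it states: "we anticipate the pCR rate to be 40% among patients with favorable VEGF/EGFR". The assumed rate in the other group is 10%. For an observed 40% unfavorable, it says that "with 92 patients in the Endo-HDR arm, the test will have 89% power".

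The caption of Table 3 opens with "Power to detect a 30% difference under various observed prevalence of unfavorable VEGF/EGFR". The rows give power for four values of that prevalence: 0.77 at 25%, 0.89 at 40%, 0.90 at 50% and 0.85 at 75%. The caption also fixes the test: "using a two-sided Fisher's exact test at significance level 0.05". It does not say how the two-sided p-value is formed.

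Section 14.2.1 sizes the trial on the primary comparison, an increase in pCR "from the 13% in the control treatment arm to 30% pCR in the Endo-HDR arm". Section 14.5 describes the imaging and biomarker analyses as exploratory.

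**The concern.** Every input to Table 3 is stated, so each row can be checked exactly. The 25% and 75% rows use the same two group sizes, 69 and 23, with the rates exchanged, so any inconsistency between them is easy to see. Table 3 and the sentence above it are the only power statement for the marker objective listed in Section 4.2, and a reader will take its figures at face value.

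A second matter is how the table relates to the primary design. The signature-specific rates are held at 40% and 10% while the prevalence changes, so the overall Endo-HDR pCR implied by each row also changes, and it need not equal the 30% in Section 14.2.1.

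The stakes are modest. Table 3 does not set the sample size or govern any decision about the trial.

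**Working it through.** **Inputs.** From Section 14.5: N = 92 in the Endo-HDR arm, pCR 0.40 (favorable) and 0.10 (unfavorable), two-sided Fisher's exact test, alpha 0.05, and prevalence of unfavorable signatures of 25%, 40%, 50% and 75%. The prevalence is described as observed, so the split of the 92 is fixed in each row.

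**Group sizes.** Unfavorable n = 92 × prevalence:

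- 25%: 92 × 0.25 = 23 exactly, leaving 69 favorable
- 40%: 92 × 0.40 = 36.8, so 36 or 37, leaving 56 or 55
- 50%: 46 and 46
- 75%: 92 × 0.75 = 69 exactly, leaving 23 favorable

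**Formula.** Power = Σ over x and y of Bin(x; n_fav, 0.40) × Bin(y; n_unf, 0.10) × 1[Fisher p(x, y) ≤ 0.05], where x and y are the numbers with pCR. The usual two-sided p sums the probabilities of all tables no more likely than the one observed, given the margins. The alternative convention doubles the smaller one-sided p.

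| Unfavorable prevalence | Favorable/unfavorable | Stated | Usual two-sided | Doubled one-sided |
|---|---|---|---|---|
| 25% | 69/23 | 0.77 | **0.810** | 0.766 |
| 40% | 56/36 | 0.89 | 0.894 | 0.871 |
| 40% | 55/37 | 0.89 | 0.903 | 0.883 |
| 50% | 46/46 | 0.90 | 0.898 | 0.898 |
| 75% | 23/69 | 0.85 | 0.848 | 0.783 |

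Under the usual test, three rows and the 89% in the text reproduce to two decimals (the 40% row with 36 unfavorable). The 25% row does not: 0.810 − 0.77 = 0.04. Doubling gives 0.77 for the 25% row but misses the 75% row by 0.85 − 0.783 ≈ 0.07.

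**Departures from the stated inputs that bring the 25% row closer.** All use the usual two-sided test.

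| Change | 25% | 40% | 50% | 75% |
|---|---|---|---|---|
| Stated in Table 3 | 0.77 | 0.89 | 0.90 | 0.85 |
| N = 92, but 22 unfavorable in the 25% row and 36 in the 40% row | 0.773 | 0.894 | 0.898 | 0.848 |
| Random (binomial) split of the 92 | 0.783 | 0.895 | 0.913 | 0.839 |
| N = 90, fixed splits | 0.781 | 0.899 | 0.889 | 0.832 |

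**Implied overall Endo-HDR pCR.** Overall = prevalence × 0.10 + (1 − prevalence) × 0.40:

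- 25%: 0.025 + 0.300 = 32.5%
- 40%: 0.040 + 0.240 = 28%
- 50%: 0.050 + 0.200 = 25%
- 75%: 0.075 + 0.100 = 17.5%

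Setting 0.40 − 0.30 × prevalence = 0.30 gives a prevalence of one-third. With a 61/31 split, the usual test has power 0.87 there.

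**The case against.** The best defence of the 25% row is that one test can produce all four printed values. With 22 unfavorable patients instead of 23, the usual two-sided test gives 0.773, and the other rows already match. A random split of the 92, or N = 90, also comes within 2 points on every row. This shows that a slip of one patient is a possible cause. It does not make the row right. A quarter of 92 is exactly 23, and the random split and N = 90 both depart from the stated observed prevalence and the stated 92. Both also give 0.78 for the 25% row, not 0.77.

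Three stronger readings are tempting, and the documents support none of them.

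- *The table mixes two test conventions.* Doubling does fit the 25% row, but it is one candidate cause among several. The protocol mentions no doubling, and the one-patient slip explains the figure equally well.
- *The rows contradict the 30% design rate.* Table 3 is a sensitivity grid, "under various observed prevalence of unfavorable VEGF/EGFR and/or hypoxia marker signatures". Its rows are alternatives, at most one can occur, and nothing in Section 14.5 ties them to "30% pCR in the Endo-HDR arm". The 25% and 40% rows imply rates within 2.5 points of 30%. Only the 75% row is far away, at 17.5% against 13% for control.
- *The 75% row overstates power by about 14 points.* Forcing the arm average to 30% with a 30-point gap gives rates of 52.5% and 22.5% and power of 0.71. Those rates appear nowhere in the documents. On the protocol's own 40% and 10%, the printed 0.85 is correct.

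It also stands that the error is conservative and the analysis exploratory.

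**Conclusion.** One of the four power figures in Table 3 is wrong on its stated inputs. The 25% row should read 0.81, not 0.77, an understatement of about 4 percentage points. The other three rows and the 89% in the text are correct under the usual two-sided Fisher test. This rests on taking the protocol literally: exactly 92 patients, the split fixed at the observed prevalence, and the usual definition of the two-sided p-value. The cause of the error cannot be established from the documents.

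The implied overall pCR rates are a matter of interpretation and not an error. The 40% and 10% rates agree with the 30% design rate only near one-third unfavorable prevalence, so the 0.85 in the 75% row belongs to a scenario in which Endo-HDR does far less well than the primary design assumes. The point is minor: no sample size, decision rule or analysis changes.

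**What to change.** In Table 3, change the 25% row from 0.77 to 0.81. State in the caption that the p-value is the usual two-sided Fisher p (the sum over tables no more probable than the one observed). Keep the 40% and 10% rates and the other three rows.

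Optionally, add a note below the table: these rates imply an overall Endo-HDR pCR of 32.5%, 28%, 25% and 17.5% at 25%, 40%, 50% and 75% unfavorable prevalence; they match the 30% in Section 14.2.1 only near one-third; and the 75% row is therefore far from the primary design assumption.

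The cost is a few minutes of recalculation and an edit to one table, with no effect on trial conduct.

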Figure 3. Representative H&E stained histopathologic sections at 4X magnification from patients who exhibited a complete pathologic response to Endo-HDR (a-e) and conventional external beam radiation (f-j). All images are taken from the region of the rectal wall where the tumor was located prior to neoadjuvant therapy. All insets are shown at 20X magnification. First Row – At the mucosa, extensive ulceration (solid arrows) is apparent after Endo-HDR (a), while the mucosa remains intact (solid arrows) after conventional CRT (f). Hyalinization of the lamina propria (asterisks) is also evident after Endo-HDR (a). Second Row – In the submucosa, marked hypertrophy and sclerosis of vessel walls can be seen following Endo-HDR (b), while only slight hypertrophy of vessel walls is seen after conventional CRT (g). Third Row – Within the muscularis propria, the more superficial interna layer can be seen to exhibit degeneration and atrophy after Endo-HDR while the externa layer remains largely intact (c); in a contrary fashion, following conventional CRT, it is the externa layer that exhibits more prominent degeneration compared to the interna (h). Fourth Row – At the level of the subserosa, vessel walls appear normal in patients treated with Endo-HDR (d), but distinctly hypertrophied in patients treated with conventional CRT (i). Fifth Row - The serosa demonstrates few adhesions (asterisk) after treatment with Endo-HDR (e), in contrast to the extensive adhesions (asterisks) present after treatment with conventional CRT (j).

We propose comparing Endo-HDR versus standard NCRT (IMRT) for stage II/III low rectal cancer (<14 cm from the anal verge). We have focused on patients with distal rectal carcinomas and include patients likely to undergo an APR as they are at highest risk for local failure after TME and most would be excluded in the current national PROSPECT trial. We have also incorporated staging FDG-PET/CT and MRI to exclude any patients with radiographic evidence of pathologic inguinal or iliac lymphadenopathy (defined as >1.5 cm, necrotic on MRI as detailed in the MERCURY study, or suspicious on PET/CT) (29).

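### The exploratory SUV-response analysis names no treatment term, so an arm difference in SUV change would inflate or mask the SUV-pCR association

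*Combined protocol and SAP*

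**What the plan says.** The imaging objective is listed first in section 4.2: "Test whether clinical response based on functional imaging (PET, MRI) pre/post radiation (Endo-HDR vs. CRT) predicts for pathologic complete response". The method is in the last paragraph of section 14.5. For SUV, "we will compare the change of SUV pre- and post-treatment between responders and non-responders using a two-sample t-test". The fallback is that "Non-parametric Wilcoxon test will be considered when the data are not normally distributed". For a binary response outcome, the plan adds an ROC curve from a logistic model "in which the imaging marker will be entered as an independent variable". No stratum, covariate or interaction for treatment is named in any of these.

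The same section handles the tissue markers differently. For VEGF/EGFR it plans "testing the interaction of the treatment group and VEGF/EGFR status using a logistic regression model where pCR is the dependent variable".

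Section 14.5 also states the status of this work: "The analysis of correlative endpoints of imaging and biomarkers will be exploratory". It gives no significance level for the SUV test and does not define responder.

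**The concern.** Randomization balances what is measured before treatment. SUV change is measured after it and may itself depend on the treatment received. The protocol gives reasons to expect this. One arm receives four brachytherapy fractions on consecutive days without chemotherapy; the other receives 28 external-beam fractions with capecitabine. The histology legend in section 3.3.1 reports that, at the former tumor site, "extensive ulceration (solid arrows) is apparent after Endo-HDR (a), while the mucosa remains intact" after conventional chemoradiation.

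The design also assumes that pCR differs by arm. If SUV change and pCR both differ by arm, responders and non-responders contain different mixes of the two treatments. A comparison that ignores arm then adds a between-treatment difference to whatever association exists within each treatment. Depending on the direction of the SUV difference, this could make imaging look predictive when it is not, or hide real prediction. Section 10.1 hopes that functional imaging will help predict pCR after each of the two treatments, which is a within-treatment question.

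**Working it through.** **Inputs from the documents.** Section 14.2.1: 92 Endo-HDR and 46 control patients; pCR 30% and 13%. Section 14.5: the tests described above.

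**Assumptions, because the documents give no value.** Responder means pCR. The SUV test is two-sided at 5%. SUV change is normal with equal SD in both arms. The arm difference in mean SUV change is d within-arm SDs, shown over a range.

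**Check of the inputs.** The plan states no figure for the SUV analysis, so there is none to reproduce there. For the primary endpoint, exact enumeration of the one-sided Fisher test at 0.1 with 46 and 92 patients and 13% and 30% gives 80.2% power, against the stated 80%.

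**Step 1: arm mix by response.**
- Responders: 92 × 0.30 + 46 × 0.13 = 27.60 + 5.98 = 33.58. The Endo-HDR share is 27.60 / 33.58 = 82.2%.
- Non-responders: 92 × 0.70 + 46 × 0.87 = 64.40 + 40.02 = 104.42. The Endo-HDR share is 64.40 / 104.42 = 61.7%.
- Difference in share: 82.2% − 61.7% = 20.5 percentage points.

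**Step 2: bias with no within-arm association.** The expected responder-minus-non-responder difference is 0.205 × d SD. The expected AUC is 0.5 + 0.205 × [Φ(d/√2) − 0.5]. For d = 1, Φ(0.707) = 0.760, so AUC = 0.5 + 0.205 × 0.260 = 0.553.

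**Step 3: false-positive rate.** Simulation, 40,000 trials per setting, no within-arm association. The adjusted analysis regresses SUV change on pCR and arm.

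| d (SD) | Spurious difference (SD) | AUC | t-test ignoring arm | Adjusted for arm |
|---|---|---|---|---|
| 0 | 0 | 0.500 | 5.0% | 5.0% |
| 0.25 | 0.05 | 0.514 | 5.7% | 5.1% |
| 0.5 | 0.10 | 0.528 | 7.8% | 4.9% |
| 1.0 | 0.21 | 0.553 | 15.0% | 5.0% |
| 1.5 | 0.31 | 0.573 | 23.9% | 5.1% |

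Independent repeats at 1.5 SD gave between 23% and 24%. With equal pCR in both arms and d = 1, the unadjusted rate is 4.9%: both differences are needed for bias.

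**Step 4: masking.** Now assume a true within-arm difference of 0.6 SD between responders and non-responders, with the arm shift in the opposite direction. The expected unadjusted difference is 0.6 − 0.205 × d: 0.50, 0.40 and 0.29 SD for d = 0.5, 1.0 and 1.5. Simulated power:

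| Opposing shift (SD) | t-test ignoring arm | Adjusted for arm |
|---|---|---|
| 0 | about 84% | about 83% |
| 0.5 | about 67% | about 83% |
| 1.0 | about 43% | about 83% |
| 1.5 | about 20-22% | about 83% |

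If no shift exists, adjusting costs about one percentage point of power.

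**The case against.** Several points on the other side are sound.

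- **The text does not say that the arms are pooled.** A reader might infer that pooling is the stated plan. It is not stated: section 14.5 refers to all patients in both arms only for VEGF/EGFR, and the imaging objective in section 4.2 mentions both treatments. What the documents support is that the handling of arm is not specified. Still, a two-sample test of responders against non-responders, followed as written, has no place for arm.
- **The analysis is exploratory.** No decision rule or sample size depends on it. This limits the importance of the point but does not make an unadjusted estimate easier to interpret.
- **The SUV difference by arm is unknown.** The histology legend contains no SUV data, and section 10.1 gives one rescan window after radiotherapy, 4-8 weeks, without distinguishing the arms. The range of d is therefore illustrative. Even at 1.5 SD the spurious AUC is only 0.57, which few would take for useful prediction.
- **Responder is not defined in the SUV sentence.** Section 7.4.3 calls tumor regression grades 1-2 a good response. The arm mix in the working holds only if responder means pCR.
- **An arm effect on SUV may be part of the response.** An overall ROC curve answers a legitimate question about prediction across both treatments. That is true, but it is a different question from prediction within a treatment, and the plan does not say which is meant.

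A reader might also infer that any association found would be false. That requires no association within either arm. Section 10.1 reports earlier data in which SUV change predicted downstaging after chemoradiation, so a distorted association is at least as likely as a wholly spurious one.

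**Conclusion.** The point holds as an omission in an exploratory analysis: neither the SUV comparison nor the ROC model names treatment, although the same section gives VEGF/EGFR a treatment interaction. Under the design's own pCR rates, an arm difference in SUV change would bias the association in either direction.

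The size is conditional on the assumptions listed in the working. For arm shifts up to 1 SD, false positives rise to at most about 15%; 23-24% needs a 1.5 SD shift that nothing in the documents establishes. Loss of power under an opposing shift is potentially the larger harm, but it rests on a further assumed 0.6 SD effect. The documents do not support saying that the imaging result will be false, or that the trial's main conclusion is at risk: the primary pCR comparison is unaffected.

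**What to change.** In section 14.5:

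1. State that responder means pCR in the SUV analysis.
2. Replace the unadjusted t-test with an arm-adjusted comparison (SUV change regressed on pCR and arm), or a test stratified by arm. Specify the Wilcoxon fallback in stratified form too.
3. Include arm in the logistic model with the imaging marker.
4. Report the SUV difference and the ROC curve within each arm.
5. Show the arm-by-SUV interaction as descriptive only.

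The cost is one degree of freedom for arm, or two with the interaction; no new data are needed. The control arm expects only about 6 responders (46 × 0.13 = 5.98), so its SUV difference and AUC, and the interaction, will be imprecise and should be presented with confidence intervals and that caution.
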